All laboratory assessments (and some treatment sessions) will be conducted in our Duke Young Child Laboratory in the Center for Developmental Epidemiology, located on bus lines including free public bus lines with free parking and available childcare. The laboratory consists of a cheerful playroom where children can use toys and a comfortable interviewing room (adjacent to playroom) where parents will be interviewed (c) and children will complete the laboratory mood induction task (d). Parents will be able to use seating in the playroom during the mood induction task to complete the surveys (b).

The daily pain diaries (a) will be given to participants to fill out where ever works best for the participants. They will be given these three daily surveys to fill out, within a paper flip booklet which the subject will turn in to the researchers after the completing the Daily Pain Diaries.

We also send out a short questionnaire to our subject's teachers at two time points (which we are currently getting permission to do within our main study consent form that the parent fills out and signs, along with giving us the teachers name, school, address, e-mail address, and phone number). First we plan to contact the subject's teacher via e-mail to see if they would be willing to fill out these questionnaires, and if they e-mail us back, letting us know that they would like to participate, we will send the teacher a questionnaire link, via Duke Qualtrics, prior to the subject starting their investigational treatment sessions. We would then e-mail the teacher a second time, after the subject has completed all 10 of the treatment sessions, to see if they would be willing to again fill out these questions via a Duke Qualtrics link.

Assessment Measures:

Feasibility: Hypotheses A.H2_a, A.H2_b/B.H1_a, B.H1_b.

We will keep a continuous measure of session attendance with missed sessions that are rescheduled within a two-week window (to account for vacations, etc.). Homework practice is recorded by therapists at every session (number of practice sessions completed regardless of degree of completion) and quality of homework (none, attempt, completed) to provide a continuous measure of treatment feasibility.

Clinical Significance: Hypotheses A.H3_a /B.H3_a, B.H3_b, B.H3_c, B.H3_d

Treatment efficacy is assessed along dimensions of: a) physical pain, b) impairment, and c) emotion-regulation (exploratory).

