Pain: Children and their caregivers will be trained to complete pain ratings using a Daily Pain Diary which contains a Pain Thermometer to rate pain experienced and the Self-Assessment Manikin (SAM) scale to rate emotional experience. Caregivers are trained to use the child's verbal reports, facial expressions, and behaviors to make these ratings. Children make their ratings twice daily: in the morning and before dinner. Parents rate their child's pain three times daily: in the morning, before dinner, and at the end of the day. The end of day survey contains additional questions asking about the child's overall pain experience throughout the entire day, as well as their distress and mood. These ratings are completed for one week prior to treatment and one week post-treatment, on a daily basis. Pain ratings are collected during 2 of the 10 weeks of treatment.

Impairment: Change in function will be assessed by diagnostic interviews and global ratings of clinical and functional change by reviewers blind to the randomization on the basis of these interviews, functional status as reported in pain/emotion diaries, and medical chart review of frequency of visits and physician contacts.

Diagnostic Interviews: [name] is the leading author of the Preschool Age Psychiatric Assessment (PAPA), one of the most widely used and reliable semi-structured interviews for diagnosis of young child psychopathology. The caregiver reports on his or her child's family context, psychiatric diagnosis, self-regulatory abilities including sensitivity to sensation, developmental history, and impairment. Numerous studies have established its predictive validity and sensitivity to change with intervention. Impairment is assessed across multiple domains as well as the perceived cause of impairment (e.g. due to physical symptoms). To shorten administration, modules chosen are based on frequency of somatic symptoms and include ADHD, somatization, social phobia, separation anxiety, generalized anxiety, and depression.

Functioning ratings in daily pain diaries – Parents are asked to provide an assessment of their child's functioning three times per day. In the morning (beginning of day) and afternoon (before dinner), they rate their child's ability to pay attention and have fun whilst experiencing tummy pain. At the end of the day, they provide a detailed report of their child's physical and emotional functioning over the course of the day.

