Global Ratings: Clinical Response - At pre and post-assessment, clinical status and improvement will be rated by blind raters on the eight-point Clinical Global Impression Scale Improvement. Participants who are rated as clinically improved or much improved in the area of physical symptoms will be considered treatment responders.

Global Ratings: Functioning - Global functioning will be rated by a rater blind to treatment status using the Children's Global Assessment Scale, a 100-point scale with 1 being most impaired and 100 being

least impaired. A score of 41–50 indicates a moderate degree of interference in functioning in most social areas or severe impairment of functioning in one area, whereas a score of 61–70 indicates generally functioning well with some difficulty in a single area. Scores of 70 or above will be considered responders.

Emotion Regulation: Emotion regulation is measured at pre- and post-treatment with our mood induction paradigm and child-reported emotional valence ratings in the daily pain diaries.

Mood induction laboratory paradigm - We employ a standardized mood induction paradigm for young children (viewing film clips). Additionally, we have children self-report on their emotions, pain, and hunger level, as well as changes in body sensation (movement of their heart and gut), throughout the task. Figure 4 provides a graphical representation of the mood induction task. To better assess the subject's physiological state while watching these mood inducing video clips, subjects will be hooked up to a BioPac machine which will collect the following physiological data: EEG, ECG, Galvanic Skin Response, and Respiration. The film clips include exciting clips,, sad clips, disgusting clips, fearful clips, and happy clips. If children have successfully learned to discriminate and regulate emotional experiences, they should 1) complete the lab task despite increased emotion, 2) change ratings of body sensation and emotion with each clip, but not pain

Child-reported emotional valence - We have children use the SAM scale in their daily pain diaries to assess their daily emotional state. By giving daily ratings of their emotional state, their pain state, and combining these with parent reports of the same, we can examine increasing segregation of ratings of pain from those of emotional experience.

R-33 Phase

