As of February 2016, we have completed the R-21 phase of The Feeling and Body Investigators (FBI) Study (N=26) and have received approval to continue into the R-33 phase of the study. We are currently in the process of analyzing the data collected during the R-21 phase of the study, updating materials based on subject feedback, and preparing to begin recruitment of our next 100 subjects (N=100).

The R-33 phase, called The Duke Tummy Pain (DTP) Study, will differ from the R-21 phase in that we will be comparing our Investigational Treatment (Feeling and Body Investigator Treatment, or FBI) to a control treatment (Caregivers in Action Treatment, or CIA). Recruitment, eligibility criteria, and assessment strategies will stay the same as they were in the R-21 phase. Subjects recruited into the R-33 phase will be randomized to either the experimental treatment (FBI) or the control treatment (CIA), but both groups will receive the same number of treatment sessions (10), with 8 sessions conducted in our lab space and 2 sessions conducted via Skype.

The R33 period will repeat the goals of the R21 period using an improved intervention, a large sample to discern statistical and clinical significance, and a randomized design with a parent-psychoeducation comparison condition. Endpoints include quantification of whether this intervention can have broad impact: using primary care practices to screen and subsequently treat abdominal pain early in the life and disorder cycle.

Those who receive the FBI Investigational Treatment will still be trained using an improved version of the FBI R-21's interoceptive exposure (the manipulation of visceral sensation) to explore "body mysteries" in a playful, investigative context, designed to increase curiosity about body functions. The CIA (treatment as usual) focuses more on the parent, who will receive a psychoeducation comparison condition. Parents will receive educational handouts, similar to what they would receive from a Pediatricians office, and the therapist will review these materials with the parent, while the child is playing in the room.

As of November 2016, [name] (a Co-PI on this study) has taken a position at NYU and will no longer be working with subject's PHI for this study. [name] will now be moved to our "Outside Duke Key Personnel" and is still involved with Duke, but as an adjunct professor.

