Those Assigned to FBI: Children will lead the sessions (the "FBI missions") both to maximize their engagement and minimize their fears of body-focused exposures. While part of the treatment is gently nudging children to do things that produce a somatic sensation, it is critical that children feel safe and thus they can terminate a session whenever they wish. Our typical approach to such a request is to first attempt to titrate the exposure down to a level that is acceptable for the children until they are excited about the mission. In the event of continued refusal, we use the session to hone our "observational skills" or go into "investigative mode": figuring out why today is such a rough day. Thus, sessions are always productive no matter what the emotional state of the child.

Those Assigned to CIA: These sessions will be focused on the psychoeducation of the parent, but the child will be in the room playing while the therapist is reviewing the educational materials with the parent. There will be a 10-lesson educational curriculum designed to educate caregivers about the management of their child with FAP. To create the curriculum for CIA, we reviewed patient handouts for exemplary pediatric gastrointestinal programs, professional healthcare organizations, and companies that supply the patient handouts incorporated into electronic medical record systems (e.g. Maestro). Following the review of these materials, we extracted the primary themes and lessons and organized them into a session-by-session curricula.

Assessment Procedures

**The same as the R-21 Phase, except for adding a 6 month follow up battery of questionnaires which will be sent to the parent via an e-mail link using Duke Qualtrics. These questionnaires will be the same as the questionnaires that caregivers fill out during the Lab 1 and Lab 2 portion of this study.

Assessment Measures:

Feasibility: Hypotheses A.H2_a, A.H2_b/B.H1_a, B.H1_b.

We will keep a continuous measure of session attendance with missed sessions that are rescheduled within a two-week window (to account for vacations, etc.) counted (range: 0-10). Homework practice is recorded by therapists at every session and rated by two independent blind raters on frequency (number of practice sessions completed regardless of degree of completion) and quality of homework (none, attempt, completed) to provide a continuous measure of treatment feasibility.

Clinical Significance: Hypotheses A.H3_a /B.H3_a, B.H3_b, B.H3_c, B.H3_d

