Treatment efficacy is assessed along dimensions of: a) physical pain, b) impairment, and c) emotion-regulation (exploratory).

All assessments will be the same as in the R-21 Phase

Selection of Subjects

- List inclusion/exclusion criteria and how subjects will be identified.

The primary care clinic where we recruited during the R-21 sees both privately insured and Medicaid children. The staff saw 1798 children between the ages of 5 and 9 years old in a previous study conducted at this clinic, The Preschool Anxiety Study. Based on our preschool cohort data (n=918) drawn from this primary care clinic, we expect 1) 8% to meet study criteria or 144 children. Assuming that 20% refuse to screen (approximately 30), we plan to screen 174 children. For the R33, we need to recruit 140 individuals to enroll 100 subjects; it will take 70 weeks to recruit this number (1.3 years). To get our N of 100 we plan to "consent to screen" close to 2,000 potential subjects. Having found that we had recruited most of the eligible subjects from the Picket Road Pediatric Clinic during the R-21 phase, we began recruiting from Duke's Southpoint Pediatric Clinic as well in late 2015. For the R-33 phase we plan to recruit from Duke's Southpoint Clinic, Durham Pediatrics, and potentially at Picket Road Pediatric Clinic once additional potential subjects have aged in. Further, based on our cohort data, we expect roughly equal numbers of males, females, ages, and those with a psychiatric disorder. We also found that the racial distribution of abdominal pain is roughly equivalent to the racial

and ethnic distribution of the Raleigh/Durham metropolitan region (45% Caucasian, 45% African-American, and 10% other underrepresented minorities). Thus, we are able to recruit a representative sample and make the intervention available to all who would benefit.

Subject Recruitment and Compensation

- Describe recruitment procedures, including who will introduce the study to potential subjects. Describe how you will ensure that subject selection is equitable and all relevant demographic groups have access to study participation (per 45 CFR 46.111(a) (3)). Include information about approximately how many DUHS subjects will be recruited. If subjects are to be compensated, provide specific prorated amounts to be provided for expenses such as travel and/or lost wages, and/or for inducement to participate.

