Procedures to preserve confidentiality. Interview schedules and tapes will be closely protected at all times. After collection, coding, and review for accuracy by the project coordinator, data are entered double-entered into computer files at our offices at Duke, except for the ePAPA which are computerized and do not require double data entry. The schedules and tapes are then stored in locked storage facilities. Participant information on the computer files is identified only by a study-specific identification number. Only approved research staff has access to the data. All faculty and staff have taken and passed Duke's required training modules on HIPAA regulations for protecting participants' privacy, and the Center for Developmental Epidemiology, where the study records are held, observes all approved security rules to protect the data. The Center for Developmental Epidemiology has a full-time staff member, our medical information systems manager [name], who oversees our group's HIPAA compliance.

Costs to the Subject

- Describe and justify any costs that the subject will incur as a result of participation; ordinarily, subjects should not be expected to pay for research without receiving direct benefit.

There are no costs to the subjects.

Data Analysis & Statistical Considerations

- Describe endpoints and power calculations. Provide a detailed description of how study data will be analyzed, including statistical methods used, and how ineligible subjects will be handled and which subjects will be included for analysis. Include planned sample size justification. Provide estimated time to target accrual and accrual rate. Describe interim analysis including plans to stop accrual during monitoring. Phase I studies, include dose escalation schema and criteria for dose escalation with definition of MTD and DLT.

Statistical Methods

Tests of hypotheses will be based on standard binomial models for proportions and Student's t-test or standard ANCOVA regression models as appropriate for continuous measures; ordinal data not meeting assumptions of normality will be analyzed using nonparametric Wilcoxon Mann-Whitney procedures or, in some cases, generalized linear regression (Poisson, logistic) models. For the R33, evaluations will be repeated 6-months post-treatment.

Data & Safety Monitoring

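### R33 outcomes are timed from the end of treatment, with no due date for dyads that stop early, so the FBI versus CIA comparison (B3) is open to bias if attendance differs by arm and loses precision if it does not

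*Protocol*

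**What the plan says.** The timing rules are spread over several protocol sections.

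- **Pain diaries** (Assessment Measures, Pain): "These ratings are completed for one week prior to treatment and one week post-treatment, on a daily basis".
- **Global ratings** (same part, Global Ratings): "At pre and post-assessment, clinical status and improvement will be rated by blind raters". No week is given.
- **Mood task** (Emotion Regulation): "Emotion regulation is measured at pre- and post-treatment with our mood induction paradigm".
- **Second teacher form** (Assessment Procedures): e-mailed "after the subject has completed all 10 of the treatment sessions".
- **Parent interview** (Compensation): one before and one after treatment.
- **Follow-up** (Statistical Methods): "For the R33, evaluations will be repeated 6-months post-treatment".

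Most of these rules are written under the R21 heading, but they govern R33 too. The R-33 section keeps the R21 assessment procedures apart from adding the 6-month questionnaires, and states that "All assessments will be the same as in the R-21 Phase". The planned course is the same in both arms: "both groups will receive the same number of treatment sessions (10), with 8 sessions conducted in our lab space", the other two being held by Skype. The Pain paragraph puts treatment at 10 weeks. For attendance, the R-33 Feasibility paragraph has "missed sessions that are rescheduled within a two-week window (to account for vacations, etc.) counted (range: 0-10".

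No section sets an assessment week or window counted from randomisation, a maximum treatment period, or an assessment date for a dyad that stops before session 10. The one rule on interrupted treatment (Risk/Benefit, B.2b) concerns referred cases and keeps their intervention data up to the referral. Statistical Methods names tests but no analysis set and no rule for missing outcomes. The SAP deals only with treatment completion and homework completion.

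**The concern.** Randomisation makes the arms comparable from the day of allocation, provided outcomes are then sought at the same time and from everyone. An end-of-treatment anchor ties both conditions to attendance, which happens after allocation and can respond to it. A family that attends slowly has its outcome read later. A family that stops has no stated date for most measures and, read literally, never triggers the second teacher form.

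The timing scheme was written for a single-arm development phase, where no comparison depended on it, and was carried unchanged into a two-arm trial. B3 asks whether FBI reduces pain and impairment more than control. The arms ask different things of the child: FBI exposes the child to body sensations, whereas in CIA the child plays while the parent is taught. A difference in attendance is therefore conceivable. If one arose, part of the B3 contrast would reflect who stayed and how long each child was observed.

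**Working it through.** The documents give no power calculation, effect size, SD or expected loss for FBI versus CIA, so there is no planned figure to reproduce. The inputs are:

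- *From the documents:* 100 children randomised; 10 sessions over a nominal 10 weeks; a treatment-completion target of at least 80%; a two-week window for counting rescheduled sessions.
- *Assumed:* 1:1 allocation (50 per arm), two-sided 5% test, outcome SD = 1, and the loss rates, severity gaps and rates of natural improvement below.

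**1. How far the anchor can move.** If the last session is made up at the end of its window, treatment ends at week 10 + 2 = 12. The text sets no upper limit. It also does not say that a made-up session pushes back those that follow, so typical slippage cannot be derived.

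**2. How many dyads lack a due date.** At the 80% target, 100 × (1 − 0.80) = 20 children, or 10 of 50 per arm if evenly split, may stop early and still leave the feasibility hypothesis met.

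**3. Precision if those outcomes are lost equally.** Detectable difference with 80% power, two-sample t-test:

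| Assessed per arm | Detectable difference |
|---|---|
| 50 | 0.566 SD |
| 40 | 0.634 SD |

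The normal approximation (1.960 + 0.842) × √(2/n) gives 0.560 and 0.626.

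**4. Bias if outcomes are missing for non-completers and loss differs by arm.** If non-completers are *g* SD worse than completers, the completers' mean is better than the whole arm's by (proportion lost) × *g*. The bias in favour of FBI is then (loss in FBI − loss in CIA) × *g*.

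| Loss FBI | Loss CIA | *g* = 0.5 | *g* = 1.0 |
|---|---|---|---|
| 20% | 20% | 0 | 0 |
| 20% | 10% | +0.05 SD | +0.10 SD |
| 20% | 0% | +0.10 SD | +0.20 SD |
| 10% | 20% | −0.05 SD | −0.10 SD |
| 0% | 20% | −0.10 SD | −0.20 SD |

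**5. Bias from timing alone.** Bias = (natural improvement per week) × (difference between arms in mean delay). With an assumed 0.01 to 0.05 SD per week, a 2-week difference gives 0.02 to 0.10 SD and a 4-week difference 0.04 to 0.20 SD. The slower arm benefits. With equal delay the bias is 0.

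Steps 4 and 5 are illustrations. Nothing in the documents fixes the loss rates, the gaps, the weekly rate or the sign.

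**The case against.** The strongest reply is that nothing shows attendance to differ by arm. Both arms have 10 sessions in the same format. The FBI procedures also work against drop-out: children lead, exposure is eased when they resist, and a refused mission becomes an observation session. Without an arm difference, steps 4 and 5 give zero bias. This stands. A reader might infer that the timing rule undoes randomisation or favours FBI; the documents support neither.

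The two-week window appears under Feasibility and says which sessions count as attended. It is not a rule that shifts the schedule. That also stands: one cannot infer that each missed session delays the outcome by two weeks. What remains is that no limit on treatment length is given.

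Only the teacher form is literally tied to 10 sessions, and it is not the measure named for either main B3 hypothesis. The other measures say post-treatment or post-assessment, which need not exclude a dyad that stopped, and the payments attached to post-treatment assessments give such dyads a reason to return. A reader might infer that a completers-only analysis is planned. It is not: the SAP's 10-session definition belongs to a feasibility outcome. The plan is silent on non-completers, but silence leaves collection to case-by-case judgement.

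Finally, timing from the end of treatment answers a legitimate question, the response to a delivered course. That is fair, so a strict anchor at randomisation is partly a choice. It does not meet the need for a due date for dyads that never finish. ANCOVA, which Statistical Methods allows, would remove only the part of a drop-out gap that baseline predicts, if baseline is a covariate.

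**Conclusion.** The point holds in a limited form. R33 outcome times hang on the end of treatment, that end is not bounded, and dyads that stop early have no stated assessment date. For B3 this is a risk of unknown size and direction, conditional on attendance or drop-out differing between arms. In the scenarios shown it runs from −0.20 to +0.20 SD and is zero when the arms behave alike.

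With equal behaviour, variable timing mainly adds variance, and losing 10 outcomes per arm moves the detectable difference from about 0.57 to about 0.63 SD. That figure rests on 1:1 allocation, a two-sided 5% test, 80% power and every non-completer's outcome being lost. Drop-out is the weightier part of the concern, timing the lesser. Treatment completion and homework completion, the SAP's two primary outcomes, are not touched. The change is still worth making, because R33 is also meant to test statistical and clinical significance and the remedy is cheap.

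**What to change.** In the R-33 Assessment Procedures:

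1. Set a common calendar due date with a window, counted from randomisation, for the second diary week, Lab 2, the second parent interview, the second teacher form and the 6-month questionnaires. Make the post-treatment window wide enough for the nominal 10-week course plus make-up sessions, and use the same dates in both arms.
2. Replace the 10-session trigger for the second teacher form with that due date.
3. State that these assessments are sought from every randomised dyad, whatever the number of sessions attended.

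In Statistical Methods, state that B3 is analysed by randomised arm and how missing outcomes are handled.

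The assessments and payments already exist, so the cost is wording, scheduling and some effort to trace dyads that have stopped. A few slow attenders will be assessed before their last session; a sensibly wide window keeps that number small.
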